The initial interview will begin with the interested partner, to describe the project, and to determine whether the partner meets study criteria of primary caregiver. We shall use a selfrating scale that asks about frequency of contact, involvement and care-giving responsibility for this purpose. Informed consent will then be sought from this person as well as consent for use of picture and/or voice. He or she will be shown the informed consent form. The reason for obtaining audio/video recording will be explained, i.e., to ensure that group facilitators follow correct procedures as judged by more junior facilitators who will listen to randomly selected session tapes and give feedback to facilitators. It will be emphasized that the focus of this exercise is to ensure appropriate conduct of the facilitators and that the participants' PHI will remain anonymous. Tapes will be promptly uploaded as a secure computer file, transcribed, and then the digital record will be erased Digital recording devices will be transferred across study sites via a secure carrier with a chain of custody, i.e. FedEx. Recordings will always be encrypted. All eligible participants may take as much time as needed to discuss the study with study staff, to review and discuss the consent, and to decide whether or not to participate. All members of the study staff who conduct informed consent interviews will have received appropriate training in administering the informed consent protocol. The training will emphasize that exculpatory language is not to be used. The individuals communicating information to the participant or the legally authorized representative during the consent process will provide that information in language understandable to the participant or the representative. Given possible cognitive impairments in this population, the research staff will use proven informed consent procedures. Specifically, after a Veteran has indicated willingness to participate in the study, the Veteran will be shown the informed consent form. The form will be explained, and the Veteran will be encouraged to ask questions if anything is not clear. The Veteran will then be given a brief quiz about the nature of the study. This process will be reiterated until the Veteran answers all questions on the quiz correctly and only then will the Veteran be asked to sign the consent form. Veterans will be excluded if they do not understand the study, or cannot answer all questions correctly on the quiz.

All study procedures, including consent, assessments, and intervention procedures may now be performed at the performance sites' affiliated CBOCs, in the Veteran's home, or in a neutral location, e.g., at a school library.

#### 5.4 Inclusion/Exclusion Criteria

Inclusion criteria-Veterans: Eligible Veterans must have a diagnosis of mTBI in accordance with the VA/DoD Clinical Practice Guideline for Management of Concussion/Mild Traumatic Brain Injury: injury or concussion associated with at least one of the following: brief (< 30 minutes) loss of consciousness or altered state of consciousness or post-traumatic amnesia for < 24 hours following the injury, or they either meet diagnostic criteria for PTSD based on the MINI or have trauma- or CS of at least moderate severity, as defined by either: a) PCL score >34; or b) CES score of >23. Although mTBI-related referrals will be based on a positive DVBIC screen, the diagnosis must be confirmed by Parts A-C of the VA TBI Identification Clinical Interview (Vanderploeg et al., 2012). The TBI must be either blast-related or attributable to another discrete event (e.g., fall, fight, injury) sustained during deployment in the OEF/OIF or Persian Gulf War eras. Post-concussive symptoms (e.g., sleep or memory problems, headache) must not be attributable to a subsequent injury or other pre-existing or concurrent neurologic disorder: Veterans with pre-existing or concurrent neurologic conditions (head trauma, seizures, strokes, neurosurgery, other neurologic impairments based on medical record or self-report) will be excluded. Eligible Veterans must also have a consenting, qualifying spouse/cohabiting partner and a Montreal Cognitive Assessment (MoCA) (Nasreddine,2005) score ≥ 19.The 30item MoCA screens for impairment in specific areas of cognitive functioning deemed necessary for participation in a 90-minute, structured group including attention and concentration, executive functions, language and conceptual thinking. We have specified a MoCA cut-off at the lower end of the range for mild cognitive dysfunction (≥ 19), in order to exclude Veterans with severe memory and/or other cognitive deficits, while admitting those with more mild deficits, as these represent our target population, i.e., Veterans with a history of mTBI, PTSD, and/or moderate-severe PTS or CS.

Inclusion criteria-partners: Legally married to or co-residing with Veteran for at least 6 months, with no plans for divorce or separation.

Exclusion criteria for Veterans and partners:1) a lifetime diagnosis of a major psychiatric disorder (schizophrenia, schizoaffective or bipolar disorder) or active psychosis based on the Structured Clinical Interview for DSM-IV-TR (SCID-L) (First et al., 2007); 2) alcohol or drug abuse or dependence within the past three months defined by a Short Michigan Alcoholism Screening Test (SMAST) (Selzer, 1975) ≥ 3, based on the recommended cut-off for TBI survivors (Gentilello et al.,1995) or a Drug Abuse Screening Test-10 (DAST-10) (Skinner, 1982) ≥3; 3) "severe" inter-partner violence as defined by the revised 20-item Conflict Tactics Scale

Short Form (CTS2S) (Straus & Douglas, 2004);4) a suicide attempt (actual, aborted, or interrupted) within the past six months indicated on the Columbia Suicide Severity Rating scale (C-SSRS); 5) medical condition or life event (e.g., ongoing or pending legal action in another state) that would compromise participation; 6) participation of either the caregiver or Veteran in another psychosocial intervention trial for couples six months prior to or during study or follow-up. Participation in individual psychotherapy, individual couple's psychotherapy, and pharmacotherapy are permitted: use of and starting/stopping these services will be tracked. Participants will be screened for inclusion/exclusion as described above immediately after giving consent.

## 5.5 Study Evaluations Veteran Assessment

Primary Outcome: Veteran Community Integration. Our original measure, the Sydney Psychosocial Reintegration Scale (Tate et al., 2011), normed for non-military TBI survivors in Australia, will be supplemented by the computer adaptive test version of the Community Reintegration of Injured Service Members (CRIS-CAT) (Resnik et al., 2012), developed and normed specifically for the OEF/OIF cohort. Due to a recently developed computer adaptive format, the CRIS-CAT is now a feasible measure, requiring only 10 minutes to complete.

Secondary Outcome: Veteran Emotion Regulation and Interpersonal Skills. Two measures will be used to assess change in the Veteran's use of adaptive social behaviors needed for community reintegration. Emotion regulation, currently assessed by the AX scale of the State-Trait Anger Expression Inventory (Spielberger & Sydeman, 1994), will be evaluated more directly by the Difficulties in Emotion Regulation Scale (DERS) (Gratz & Roemer, 2004), which is comprised of six orthogonal factors (nonacceptance, goals, impulse, awareness, strategies, and clarity), that together explain 56% of the variance in emotion regulation and has a Cronbach's alpha = .85 (Gratz & Roemer, 2004). In addition, the Abbreviated Duke Social Support Scale (ADSSI) (Koenig et al., 1993) will be used to measure both subjective support and social network interactions. To measure social interaction, Veterans are asked to describe their telephone and face-to-face interaction patterns and attendance at clubs and religious events during the past week outside of work. To measure subjective support, they are asked to respond to questions such as "Does it seem that your family and friends understand you most of the time, some of the time, or hardly ever?"

Mental Health/Health Behavior. Although Veteran mental health disorders/symptoms are not treatment targets in MFG-TBI, the presence/degree of PTSD or depressive symptoms, medication, substance use, physical problems and use of mental health and/or medical services may influence benefits derived from treatment. The Post Traumatic Stress Disorder Checklist-Military (PCL-M) (Weathers et al., 1996) will quantify level and type of PTSD symptoms. The 7item Combat Exposure Scale (CES) (Lund et al., 1984) will quantify level of war-zone exposure to violence, wounding and other wartime events. The 10-item form of the widely-used, reliable Center for Epidemiologic Study of Depression (CESD-10) (Irwin et al., 1999) will assess level of current depressive symptoms. The Addiction Severity Index-Lite-Veterans Administration Version (ASI-L-VA) (Cacciola et al., 2007) will evaluate alcohol and substance use and related problems. The ASI-L-VA is a widely-used semi-structured interview with well-established psychometric properties and alternate versions for baseline and follow-up administrations; scales that overlap with other measures (e.g., medical and mental health) will be eliminated. The 6-item Pain Inference Short Form (Amtmann et al., 2010) from the Patient-Reported Outcomes Measurement Information System (National Institutes of Health Roadmap initiative) and the 7-item Insomnia Severity Index (ISI) will be used to assess important Veteran health

domains not addressed by the sole current measure, the SF-8, an 8-item measure of general health. Internal consistency and reliability for the ISI is high; Cronbach's alpha = .91 (Morin et al, 2011). The Service Use Checklist ([name] et al. 2005) will document reported use and frequency of a comprehensive list of inpatient and outpatient services, as well as instances of starting/stopping psychosocial or pharmacologic treatment during the trial. For Veterans enrolled in mental health services at VA, medication and mental health service use will also be examined through the VA medical record, and we will use VA medical record data to validate the Service Use Checklist with respect to medication and mental health services in a subgroup of 60 Veterans (20 per site). Based on examination of the range and frequency of use of different medications and medication classes, we will create summary variables for use in analyses (e.g., hypnotics, antidepressants). These variables will then be evaluated for inclusion as covariates in primary analyses as articulated under "General Approach" in section 2axiv. The Memory Compensation Questionnaire (MCQ) ([name] et al., 2001) which assesses use of compensatory strategies in daily life, will be administered to MFG-mTBI-C Veterans to monitor utilization of the strategies learned in MFG-mTBI-C. The Brief Symptom Inventory – Anxiety Subscale (BSI – Anxiety) will be given to assess for symptoms of anxiety experienced within the past week. The Axis I Disorder symptomatology interviews from the Mini International Neuropsychiatric Interview (MINI) will be given to assess for current and past episodes of major psychiatric illnesses for diagnostic purposes. The Health Risk Behavior Scale (HRBS) will be administered to measure current health behaviors such as medication adherence, hygiene, and putting off medical appointments. Finally, a Life Satisfaction question will be asked to capture the participant's current quality of life and life satisfaction in general. The CESD-10, PCL, ISI, BSI, MINI, HRBS, and Life Satisfaction Scale will be given to both the Veterans and partners.

Veteran Neuropsychological Functioning will be evaluated by 3 core (Rey Auditory Verbal Learning Test (RAVLT-Vakil Blachstein,1993), and the Trail-Making Test (TMT- Bowie & Harvey, 2006) A& B, measures from the NINDS Common Data Recommendations for Neuropsychological Impairment in TBI. The Movie for the Assessment of Social Cognition (MASC) (Dziobek et al., 2006) will replace The Awareness of Social Inference Task (TASIT) (McDonald et al., 2006) as our evaluation of awareness of social inference measure. While the 2 measures are virtually identical, our research group has considerable experience with the MASC, ensuring more accurate administration and scoring.

Partners will also be administered the MASC in order to provide a control sample with which to compare the Veteran MASC data.

#### **Spouse/Partner Assessment:**

Primary Spouse/Partner Outcome: The Caregiver Burden Inventory (CBI) (Novak & Guest, 1989), a 24-item scale will evaluate caregiver burden in four areas: physical, social, emotional and time dependence burden. The CESD-10, PCL-C, SF-8, ISI, BSI, MINI, Life Satisfaction Scale, and Service Use Checklist\_will be used to evaluate depressive symptoms, trauma symptoms, mental and physical health and service use during the past 6 months. The DERS and ADSSI will also be administered to the spouse/partner.

Couples Functioning: Marital satisfaction and conflict will be evaluated by the Dyadic Adjustment Scale (DAS) satisfaction subscale (Spanier,1976), chosen over the DAS-7 (Sharpley & Rogers, 1984) as evaluating conflict as well as satisfaction (Hunsley et al.,1995). The Interpersonal Reactivity Index (IRI) (Davis, 1980) will replace the Family Crisis Oriented Personal Evaluation Scales (F-COPES) (McCubbin et al., 1985) in evaluating couples coping efficacy. Whereas the F-COPES assesse coping of the family unit (including children), the IRI assess dyadic coping with interpersonal stress and empathy, and is thus more relevant to

couples coping. It has 28 items and 3 subscales (empathic concern, personal distress, and perspective-taking). The IRI will be supplemented by the Perceived Ability to Cope with Trauma (PACT) scale (Bonanno et al., 2011) in evaluating the Veteran and partner's resilience and coping flexibility. In addition, we will administer the Post Traumatic Growth Inventory – Short Form (PTGI-SF) (Cann et al., 2010) and the Couples Assessment of Relationship Elements (CARE) (Worthington et al., 199&) to both the Veteran and partner. The IRI will be also supplemented by The Communication Patterns Questionnaire (CPQ) (Christensen & Sullaway, 1984), a self-report measure designed to assess the extent to which couples make use of various interaction strategies during conflict. Subjects are instructed to rate the use of each of 25 items, allowing researchers to "type" couples as high in demand/withdrawal, avoidant, and mutual constructive or destructive communication patterns. These typologies will be shared and discussed with couples in the individual joining sessions in order to develop individual goals for each couple. These measures will be administered to both partners. The Veteran assessment takes 120-150 minutes at baseline, and 80-95 minutes at post-treatment and 6-month follow-up. While most Veterans tolerate comparable assessments administered by skilled examiners, the assessment can be divided into 2+ sessions as needed. The spouse/partner assessment takes about 80-90 minutes to complete at baseline and 75 minutes for follow-up assessments. Wellknown measures such as the SCID-L have not been reproduced.

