**Assessment:** Participants will be assessed pre- and post-treatment and 6 months post-treatment (*Table 5 below*). Partners will be assessed within 2 weeks of the corresponding Veteran assessment. Assessors will be trained to reliably administer all clinical instruments, using the PI, a psychologist or psychiatrist experienced with these measures, as a 'gold standard.' [name], neuropsychologist based at the VAMHCS's, will establish reliability on the VA TBI Identification Clinical Interview through independent ratings of 10 interviews and will then supervise the RA at their site on administration and scoring of this interview and other neurocognitive measures on a weekly basis. An *Assessment Committee* comprised of Drs. [name], and [name] will meet bi-weekly to plan and implement training, monitor reliability via periodic checks, and implement corrective procedures as needed.

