**Table 5: Veteran and Partner Assessment** 

	Pre-treatment	Post-treatment	6-month		
Veteran Assessment					
Community Integration					
Sydney Psychosocial Reintegration Scale and CRIS-	X	Χ	Х		
CAT*	^	٨	^		
Emotion Regulation/Interpersonal Skills					
DERS (emotion regulation)	X	Χ	Χ		
Duke Social Support Scale (use of supports)	X	X	Χ		
Health Behavior	X	Χ	Χ		
CES-D-10 (depression) a	X	X	Χ		
PCL-M (PTSD) Checklist a	X	Χ	Χ		
Combat Exposure Scale a	X				
PROMIS-PI (pain)	X	Χ	Χ		
ISI (insomnia)					
Service Use Checklist a	X	X	Χ		
Addiction Severity Index a	X	Χ	Χ		
Memory Compensation Questionnaire a	X	Χ	Χ		
BSI Anxiety subscale	X	X	Χ		
MINI (Axis I Disorders)	Χ	Χ	Χ		

	.,	.,		
Life Satisfaction Scale	X	X	X	
Health Risk Behavior Scale	X	X	Χ	
Neuropsychological				
Rey Auditory Verbal Learning test *	X	X	Χ	
Trail Making Test A,B *	X	Х	X	
MASC (theory of mind)	X	X	Χ	
Couples Functioning				
Dyadic Adjustment Scale*	Χ	X	X	
IRI	Χ	Χ	Χ	
CPQ	Χ	Χ	Χ	
PACT (coping flexibility)	Χ	X	X	
Post Traumatic Growth Inventory – Short Form	Χ	X	X	
CARE (relationship skills)	Χ	Χ	X	
Spouse/Partner Assessment				
Emotion Regulation/Interpersonal Skills				
DERS (emotion regulation)	Х	Χ	Х	
Duke Social Support Scale (use of supports)	Χ	Χ	Χ	
Neuropsychological				
MASC	Χ	Χ	Χ	
Caregiver Burden/Health	.,		.,	
Caregiver Burden Inventory	Χ	X	X	
CES-D-10 (depression) a	Χ	Χ	Χ	
PCL-C (trauma)				
ISI (insomnia)	Χ	Χ	Χ	
SF-8 (health) a	Χ	Χ	Χ	
Service Use Checklist a	Χ	Χ	Χ	
BSI Anxiety subscale	Χ	Χ	Χ	
MINI (Axis I Disorders)	Х	Χ	Χ	
Life Satisfaction Scale	X	Χ	Χ	
Health Risk Behavior Scale	Х	Χ	Χ	
Couples Functioning				
Dyadic Adjustment Scale	X	Χ	X	
IRI	Х	Χ	Χ	
CPQ	X	X	X	
PACT (coping flexibility)	X	X	X	
Post Traumatic Growth Inventory – Short Form	X	X	X	
CARE (relationship skills)	X	X	X	
B. I. L. C.	^		^	

**Bolded measure** indicates primary outcome measure. a covariate in model \* NINDS core test for TBI. Screening measures are described under 2avi above.

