We have organized the assessment schedule to correspond to our conceptual and measurement models, leading with the primary study outcome, Veteran community integration, followed by measures of the secondary Veteran outcome, emotion regulation and interpersonal skills, measures of potential covariates, i.e., measures of mental health and health behavior, and measures of Veteran neuropsychological functioning hypothesized to moderate outcomes. We have followed the same organization for caregivers, ending with our measure of couples functioning, hypothesized to mediate improvement community integration

\*Subject to re-administration (Veteran only) before start of groups to control for any changes that may occur during a particularly long interim between baseline assessment and start of the group.

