
Treatment: Multi-Family Group for mTBI (MFG-mTBI-C) consists of three sequential phases: 1) "Joining" in which the educator meets with each individual family for 2-3 sessions to evaluate ongoing problems and define treatment goals; 2) An Educational Workshop which provides information about TBI to all Veterans and families; 3) bi-monthly multifamily group meetings for 6 months (12 sessions) which provide a structured format for building problem-solving and communication skills. The educator joining with each couple also leads the group. The first two phases take approximately 2 months, for a total of 8 months of intervention. The group sessions consist of 3 components: (1) A brief (15-minute) period for socialization, unwinding and "small talk"; after 15 minutes the educator starts the "Go Round" (2) in which each couple relate briefly how the past two weeks have gone for them, including follow-up on homework or problemsolving recommendations. The educators take this opportunity to amend plans which have not been successful, offering a modification of the original or an alternative solution. Based on the Go Round, a problem or goal is selected for the current week's group exercise. Thirty-five minutes are allotted to the Go Round, including problem selection. (3) The educators then lead the group in formal problem solving, using a six step process based on brainstorming methods from organizational and business practices. Approximately thirty-five minutes are allowed to complete this process, specified below. The proceedings should be recorded on a whiteboard, to facilitate group participation and record the results.

- **Step 1.** Define the problem or goal. (MFG members & educators);
- Step 2. List all possible solutions. (All MFG members);
- **Step 3.** Discuss advantages and disadvantages of each in turn. MFG members & educators);
- **Step 4.** Choose the solution that best fits the situation. (Family);
- Step 5. Plan how to carry out this solution. (Family & educators); and
- **Step 6.** Review implementation. (Educators).

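### For partners, the 6-month look-back on service use is shorter than the roughly 8 months from baseline to post-treatment, so a brief early episode of outside care falls in no checklist window

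*Combined protocol and SAP*

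**What the plan says.** **Look-back.** In Section 5.5, the Spouse/Partner Assessment paragraph lists the partner instruments, including the Service Use Checklist, and says they cover, among other things, "mental and physical health and service use during the past 6 months". No other recall period for service use appears in the document.

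**Timing.** The Treatment paragraph of Section 5.1 says of Joining and the workshop: "The first two phases take approximately 2 months, for a total of 8 months of intervention". The Assessment paragraph of the same section says: "Participants will be assessed pre- and post-treatment and 6 months post-treatment". Table 5 lists the checklist for Veterans and for partners at those three visits only and flags it as a model covariate for both.

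**Promise.** Section 5.4, under the exclusion criteria for Veterans and partners, permits individual psychotherapy, couple's psychotherapy outside the study and medication, and adds: "use of and starting/stopping these services will be tracked".

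**Veterans.** The Mental Health/Health Behavior text of Section 5.5 says the checklist will also document "instances of starting/stopping psychosocial or pharmacologic treatment during the trial". It adds VA medical-record review of medication and mental health service use for Veterans enrolled in VA mental health services. It gives no look-back in months.

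**The concern.** A fixed 6-month recall fits the step from post-treatment to the last visit, which is 6 months long. It does not fit the step from baseline to post-treatment, which is about 2 months longer. The baseline form looks backward from month 0, and the last form looks back only to the post-treatment visit, so neither recovers the early stretch.

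Outside treatment is allowed in both arms, and treatment begun after randomization is not balanced by randomization. To judge whether an arm difference in caregiver burden, the primary partner outcome, might partly reflect help obtained elsewhere, the trial needs a complete record of that help. For partners the checklist is the only tracking instrument that the document names.

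**Working it through.** **Inputs**
- Joining plus workshop: about 2 months (Section 5.1, Treatment).
- Group phase: 12 sessions over 6 months, that is, 2 a month (same paragraph).
- Partner look-back: 6 months (Section 5.5, Spouse/Partner Assessment).
- Checklist visits: pre-treatment, post-treatment, 6 months post-treatment (Table 5).

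**Reproducing the plan's figure.** 2 + 12/2 = 8 months, which agrees with the stated total.

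**Coverage for partners, no extra wait, baseline at month 0**
- Baseline form: months −6 to 0.
- Post-treatment form at month 8: 8 − 6 = 2, so months 2 to 8.
- Last form at month 8 + 6 = 14: months 8 to 14.
- Uncovered: months 0 to 2. That is 2/8 = 25% of baseline to post-treatment, or 2/14 = 14% of baseline to last follow-up. There is no gap after post-treatment.

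**How far the 2 months can move**
- *Wait before groups start.* A footnote to Table 5 foresees a "particularly long interim between baseline assessment and start of the group" for some Veterans, but gives no length. Assuming a wait of w months, the gap is (8 + w) − 6 = 2 + w. For w = 1 it is 3 of 9 months (33%); for w = 2 it is 4 of 10 (40%). Section 5.1 starts new groups every 4-5 months, so w = 5 is taken as an assumed upper bound: 7 of 13 (54%). The re-administration in that footnote is for Veterans only and does not mark this checklist, so it does not close the partner gap.
- *Session count.* Table 7 gives 14 group sessions in all. At 2 a month that is 7 months; with an assumed 0.5 to 1.5 months of Joining the interval is 7.5 to 8.5 months and the gap 1.5 to 2.5 months.
- *Partner visit window.* Partners are seen within 2 weeks of the Veteran. If the partner's baseline fell half a month late and the post-treatment visit half a month early, 8 − 1 − 6 = 1 month would remain.
- *No gap.* This needs baseline to post-treatment to be 6 months or less, which the stated 8 months does not support.

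**What is lost inside the gap**
- Starts and ends within it: missed entirely.
- Starts within it and runs past month 2: reported at post-treatment, but the early use is not counted.
- Running at baseline and stopped within it: visible as a change between forms, without the later use.

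**The case against.** The partner sentence is a loose summary. It names several instruments and ends with one time phrase, which cannot be the recall period for all of them: the BSI Anxiety subscale covers the past week. The form is not in the document, so its actual follow-up wording is unknown. The Veteran text describes a checklist of the same name as recording starts and stops throughout the trial, and the tracking promise in Section 5.4 covers partners too. This stands as a reason for caution. It does not remove the point, because the phrase directly follows service use, is the only period given, and Section 5.4 names no method that would fill the gap.

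Four stronger readings are tempting, and the document does not support them.

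- *Early outside treatment is never captured, for anyone.* For Veterans no 6-month limit is stated, starts and stops during the trial are to be recorded, and VA records are a second source. Section 7.0 restricts enrollment to Veterans who regularly receive services from, or work at, the named sites' mental health clinics, so that source may reach many of them. What could be missed is mainly the frequency of non-VA services, and only if the Veteran form uses the same window.
- *The gap falls where control couples are sent to outside providers.* Table 7 places that referral rule in the 13 health education sessions, most of which lie inside the post-treatment look-back. Control Joining is a standard intake.
- *A third or more of the interval is uncovered.* That rests on an assumed wait, and Section 5.1 expects the design to avoid a long wait in most cases.
- *The primary comparison is at risk.* Section 5.6 treats service use as a potential covariate, chosen on imbalance at baseline. The baseline window is unaffected, and the intention-to-treat comparison does not need the later data.

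**Conclusion.** The point holds for partners and is minor. A literal 6-month look-back leaves about the first 2 of 8 months (25%) outside every checklist window, and partner services that begin and end there go unrecorded, short of what Section 5.4 promises. This assumes that the 6-month phrase is the recall period on the partner form, that the first two phases take about 2 months as stated, and that there is no extra wait; a wait adds to the gap month for month. For Veterans the recall period is unspecified and a gap is unconfirmed. The consequence is a less complete account of co-intervention when the caregiver results are interpreted. The change is worth making because it is cheap and early use is hard to reconstruct later.

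**What to change.** At the post-treatment and 6-month visits, word the Service Use Checklist for partners and Veterans to cover the period since their last study assessment. Print that date on each form, and record start and stop dates for each service. Keep the 6-month look-back at baseline. State the recall period in Section 5.5 for both groups, so that the partner text, the Veteran text and Section 5.4 agree.

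This takes the gap to zero whatever the wait before groups start. It also fixes the dates for the planned comparison of the checklist with VA records in 60 Veterans, so that disagreement there is not an artifact of mismatched periods. It adds no visit and no measure. The cost is a recall of about 8 months or more, instead of 6, at the post-treatment visit, with some loss of accuracy for the earliest services; the printed date should help to limit that.
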